10.1.1.3. Serious Adverse Event (SAE)

An SAE is defined as any untoward medical occurrence that at any dose results in one or more of the following:

- Results in death;
- Is life-threatening (i.e., the subject was, in the opinion of the investigator, at immediate risk of death from the event as it occurred); it does not refer to an event which hypothetically might have caused death if it were more severe;
- Requires inpatient hospitalization or prolongation of existing hospitalization;
- Results in persistent or significant disability/incapacity (i.e., the event causes a substantial disruption of a person's ability to conduct normal life functions);
- Congenital anomaly or birth defect in the offspring of a subject;
- An important and significant medical event that may not be immediately life threatening or resulting in death or hospitalization but, based upon appropriate medical judgment, may jeopardize the subject, or may require intervention to prevent one of the other outcomes listed above.

All CESIs, AESIs and pIMCs occurring during the trial will also be reported as an SAE.

SAEs, up to end of the main trial, will be summarized as below by vaccine group, aggregate IVX-A12, and overall:

- The number and percentage of subjects reporting SAEs by SOC and PT.
- The number and percentage of subjects reporting SAEs by SOC and PT will be repeated by age subgroup analyses category.
- The number and percentage of subjects reporting vaccine-related SAEs by SOC and PT.
- The number and percentage of subjects reporting vaccine-related SAEs by SOC and PT by age subgroup analyses category.

This document is confidential.

All AEs leading to Death will be listed.

10.1.1.4. Medically-Attended Adverse Event (MAAE)

MAAEs are defined as AEs leading to an unscheduled visit to or by a healthcare professional, including visits to an emergency department, but not fulfilling seriousness criteria.

MAAEs, up to end of the main trial, will be summarized as below by vaccine group, aggregate IVX-A12, and overall:

- The number and percentage of subjects reporting MAAEs by SOC and PT.
- The number and percentage of subjects reporting MAAEs by SOC and PT will be repeated by age subgroup analyses category.
- The number and percentage of subjects who received concomitant medication treatment for the MAAEs by ATC Level 4 and PT.

10.1.1.5. Clinical Event of Special Interest (CESI)

CESIs are defined as AEs that will be specifically highlighted to the investigator. The single CESI for this trial is a CESI of mild (Grade 1) moderate (Grade 2) to severe (Grade 3) lower respiratory tract illness (mild, moderate, or severe LRTI) caused by RSV and/or hMPV occurring in the subjects after vaccination.

CESIs, up to end of the main trial, are programmatically derived as defined in Protocol Section 10.1.3, and will be summarized as below by vaccine group, aggregate IVX-A12, and overall:

- The number and percentage of subjects reporting CESIs by SOC and PT.
- The number and percentage of subjects reporting vaccine-related CESIs by SOC and PT.

10.1.1.6. Adverse Events of Special Interest (AESI) and Potentially Immune-Mediated Disorders (pIMCs)

AESIs and pIMCs are AEs described by MedDRA preferred terms as defined in the protocol sections 10.4.4.1 and [section 16](#) of the SAP.

AESIs, up to end of the main trial, will be summarized by vaccine group, aggregate IVX-A12, and overall as follows:

- The number and percentage of subjects reporting AESIs by SOC and PT.
- The number and percentage of subjects reporting vaccine-related AESIs by SOC and PT

10.1.1.7. LRTI Events Not Caused by RSV/hMPV

LRTIs not caused by RSV or hMPV, up to end of the main trial, will be summarized by vaccine group, aggregate IVX-A12, and overall, by reporting the number and percentage of subjects by SOC and PT.

10.1.2. Laboratory Evaluations

Clinical laboratory tests including hematology, clinical chemistry, and urinalysis will be collected at screening, Days 0, 7, and 28.

Hematology and clinical chemistry, up to end of the main trial, will be summarized as below by vaccine group, aggregate IVX-A12, and overall:

This document is confidential.

Numeric laboratory parameters: Actual values and change from baseline will be summarized with descriptive statistics (n, mean, SD, median, minimum, and maximum) by visit.

Shift tables for each hematology and chemistry laboratory parameters will summarize the change in the Federal Drug Administration (FDA) toxicity grades from baseline to the maximum post-baseline up to end of the main trial and for 'all visits up to Day 28' by vaccine group, aggregate IVX-A12, and overall. Unscheduled visits will be included. The denominator for percentages is the number of subjects assessed at each parameter and visit per baseline grade and with a post-baseline assessment.

For uni-directional parameters, i.e., parameters having only low grades or only high grades, a laboratory grade of 0 will be assigned to values within the normal range. Laboratory parameters having bi-directional FDA toxicity grading will have separate shift tables for each direction. For example, white blood cells will have a separate table for shift to low grade and shift to high grade. For each bi-directional parameter, a summary of shift to low grade will assign a toxicity grade of 0 to values within or above the normal range. Similarly, a summary of shift to high grade will assign a toxicity grade of 0 to values within or below the normal range.

All laboratory summaries will be repeated by age subgroup analyses category.

Data listings, up to end of the main trial, for laboratory test results will be provided, with an indicator for values that are outside the normal range. A listing including a subset of Grade 3 and Grade 4 toxicity hematology, chemistry, and urinalysis results will be provided.

A listing will also be provided for all abnormal urinalysis results of glucose, protein, white blood cells, and red blood cells. The listing will include all adverse events within 28 days of the abnormal assessment, including if the adverse event is considered an MAAE.

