APPENDIX B TOXICITY TABLES

Standard Toxicity Grading Scales: adapted from Guidance for industry: toxicity grading scale for healthy adult and adolescent volunteers enrolled in preventive vaccine clinical trials. Food and Drug Administration [[38](#)].

Table 9 FDA Toxicity Grading Scales for Clinical Laboratory Abnormalities^a

Serum Chemistry and Hematology*	Mild	Moderate	Severe	Potentially Life-threatening
	Grade 1	Grade 2	Grade 3	Grade 4**
Urea (i.e., BUN) (mg/dL)	23 26	27 31	>31	Requires dialysis
Creatinine (mg/dL)	1.5 1.7	1.8 2.0	2.1 2.5	>2.5 or requires dialysis
Total protein hypoproteinemia (g/dL)	5.5 6.0	5.0 5.4	<5.0	
Liver function tests ALT, AST; increase by factor	1.1 2.5 × ULN***	2.6-5.0 × ULN	5.1 10 × ULN	>10 × ULN
Total bilirubin when accompanied by any increase in liver function test; increase by factor	1.1 1.25 × ULN	1.26 1.5 × ULN	1.51 1.75 × ULN	>1.75 × ULN
Total bilirubin when liver function test is normal; increase by factor	1.1 1.5 × ULN	1.6 2.0 × ULN	2.0 3.0 × ULN	>3.0 × ULN
Hemoglobin (Female) (g/dL)	11.0 12.0	9.5 10.9	8.0 9.4	<8.0
Hemoglobin (Female) change from baseline value (g/dL)	Any decrease 1.5	1.6 2.0	2.1 5.0	>5.0
Hemoglobin (Male) (g/dL)	12.5 13.5	10.5 12.4	8.5 10.4	<8.5
Hemoglobin (Male) change from baseline value (g/dL)	Any decrease 1.5	1.6 2.0	2.1 5.0	>5.0
WBC increase (cell/mm ³)	10,800 15,000	15,001 20,000	20,001 25,000	>25,000
WBC decrease (cell/mm ³)	2,500 3,500	1,500 2,499	1,000 1,499	<1,000
Lymphocytes Decrease - cell/mm ³	750 1,000	500 749	250 499	<250
Neutrophils Decrease - cell/mm ³	1,500 2,000	1,000 1,499	500 999	<500
Eosinophils - cell/mm ³	650 1500	1501 5000	>5000	Hypereosinophilic syndrome
Platelets decreased (cell/mm ³)	125,000 140,000	100,000 124,000	25,000 99,000	<25,000

CONFIDENTIAL

Abbreviations: ALT, alanine transaminase, AST; aspartate transaminase; BUN, blood urea nitrogen; WBC, white blood cell.

* The laboratory values provided in the tables serve as guidelines and are dependent upon institutional normal parameters. Institutional normal reference ranges should be provided to demonstrate that they are appropriate.

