** The clinical signs or symptoms associated with laboratory abnormalities might result in characterization of the laboratory abnormalities as Potentially Life Threatening (Grade 4). For example, a low sodium value that falls within a Grade 3 parameter (125-129 mE/L) should be recorded as a grade 4 hyponatremia event if the subject had a new seizure associated with the low sodium value.

--- A" is the upper limit of the normal range.

Values provided in this table will be included in vaccination pause rules for the trial.

Table 10 FDA Toxicity Grading Scale for Vital Sign Abnormalities

Vital Sign Abnormalities*	Mild		Moderate	Severe	Potentially Life-threatening
	Grade 1		Grade 2	Grade 3	Grade 4
Tachycardia (bpm)	101	115	116	130	>130
Bradycardia (bpm)**	50	54	45	49	<45
Hypertension (systolic) (mm Hg)	141	150	151	155	>155
Hypertension (diastolic) (mm Hg)	91	95	96	100	>100
Hypotension (systolic) (mm Hg)	85	89	80	84	<80
Respiratory Rate (breaths per minute)	17	20	21	25	>25
					Intubation

Abbreviations: bpm, beats per minute; ER, emergency room.

* Subject should be at rest for all vital sign measurements.

** When resting heart rate is between 60 – 100 beats per minute. Use clinical judgment when characterizing bradycardia among some healthy subject populations, for example, conditioned athletes.

Table 11 FDA Toxicity Grading Scale for Urinalysis Abnormalities

Urinalysis Abnormalities*	Mild	Moderate	Severe	Potentially Life-threatening
	Grade 1	Grade 2	Grade 3	Grade 4
Protein	Trace	1+	2+	Hospitalization or dialysis
Glucose	Trace	1+	2+	Hospitalization for hyperglycemia
Blood (microscopic) (rbc/hpf)	1 - 10	11 - 50	>50 and/ or gross hematuria	Hospitalization or PRBC transfusion

Abbreviations: hpf, high power field; PRBC, packed red blood cells; RBC, red blood cells.

* The laboratory values provided in the tables serve as guidelines and are dependent upon institutional normal parameters. Institutional normal reference ranges should be provided to demonstrate that they are appropriate.

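### SAP 10.1.2 never mentions the protocol's hemoglobin fall-from-baseline grades, and its in-range rule, read literally, tabulates a Grade 2 or 3 fall that stays in range as Grade 0

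*SAP*

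**What the plan says.** **Protocol, Appendix B, Table 9.** Each sex has an absolute-value row and a separate change-from-baseline row for hemoglobin. The change rows have the same cut-offs for men and women. Grade 1 is printed as "Any decrease 1.5" (the dash was lost in text extraction), meaning any fall up to 1.5 g/dL. Grade 2 is 1.6 to 2.0, Grade 3 is 2.1 to 5.0 and Grade 4 is above 5.0. Nothing restricts these rows to values outside the normal range. The absolute Grade 1 band is 12.5 to 13.5 g/dL for men and 11.0 to 12.0 for women. A footnote says "The laboratory values provided in the tables serve as guidelines and are dependent upon institutional normal parameters".

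**SAP 10.1.2, Laboratory Evaluations.** Samples "will be collected at screening, Days 0, 7, and 28". For each hematology and chemistry parameter, shift tables show the change in "toxicity grades from baseline to the maximum post-baseline up to end of the main trial", with percentages taken within each baseline grade. Where a parameter is graded in one direction only, the rule is that "a laboratory grade of 0 will be assigned to values within the normal range". The section also plans by-visit summaries of change from baseline, including the minimum and maximum, a full laboratory listing, and a listing of Grade 3 and 4 results.

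**SAP section 12** lists four changes from the protocol analysis. None concerns laboratory grading.

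**The concern.** Hemoglobin has only low grades in Table 9, so the SAP's one-directional rule covers it, and no exception is written. A subject with a high-normal baseline can lose more than 2 g/dL and still finish in range. The protocol gives that fall a grade, and the SAP rule as worded sets it to 0.

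The shift-table layout does not suit the change row either. A change from baseline is zero at baseline by construction, so it has no baseline grade to shift from. The SAP does not say how the two hemoglobin rows combine, or which of them feeds the Grade 3/4 listing. Two programmers following the text could therefore produce different hemoglobin tables and different listings.

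Clinical safety laboratory parameters are a secondary safety endpoint. What is at stake is whether events that the protocol grades appear as graded events in the report.

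**Working it through.** The plan states no figure on this point, so there is none to reproduce.

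**1. The conflict, by arithmetic from Table 9**
- Man, 17.0 to 14.5 g/dL: fall = 17.0 − 14.5 = 2.5, inside 2.1 to 5.0, so Grade 3 by change. The value 14.5 is above 13.5, so it has no absolute grade. If 14.5 is in the laboratory's range, the SAP grade is 0.
- Man, 16.0 to 13.8 g/dL: fall = 2.2, also Grade 3 by change and Grade 0 by the SAP rule when 13.8 is in range.

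**2. Who can be affected**

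The documents do not give the normal range. Assume that it starts one reporting unit above the absolute Grade 1 band: 13.6 g/dL (men) and 12.1 g/dL (women). The lowest baseline from which a Grade 3 fall can end in range is then:
- men: 13.6 + 2.1 = 15.7 g/dL
- women: 12.1 + 2.1 = 14.2 g/dL

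**3. Share staying in range after a true fall**

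Assumed, not in the documents: baseline normal with mean 14.8 and SD 1.1 (men), mean 13.5 and SD 1.0 (women). With lower limit L and fall d, the share is P(Z > (L + d − mean)/SD).

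| | d = 2.1 | d = 2.5 |
|---|---|---|
| Men | (15.7 − 14.8)/1.1 = 0.82; 21% | (16.1 − 14.8)/1.1 = 1.18; 12% |
| Women | (14.2 − 13.5)/1.0 = 0.70; 24% | (14.6 − 13.5)/1.0 = 1.10; 14% |

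The range is 12% to 24%. These shares are conditional on such a fall having occurred.

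**4. In-range Grade 3 falls from noise alone**

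This is a simulation with the same distributions, no vaccine effect, one baseline draw and two post-dose draws (Days 7 and 28), and values rounded to 0.1 g/dL. Expected subjects per 250 with a Grade 3 fall and every post-dose value in range:

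| Within-subject SD (assumed, g/dL) | Subjects per 250 |
|---|---|
| 0.3 | about 0 |
| 0.4 | 0.04 to 0.05 |
| 0.5 | about 0.5 |
| 0.6 | about 2 |

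Grade 2 falls are not in these counts.

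**5. What the change row itself yields at Grade 1**

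With no true change and no ties, Day 0 fails to be the lowest of three exchangeable values with probability 2/3. That is the ceiling for any decrease at two scheduled post-dose draws, and it needs no SD. Simulated share of subjects whose worst change grade is exactly 1:

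| SD (assumed, g/dL) | Rounded to 0.1 g/dL | Unrounded |
|---|---|---|
| 0.1 | 51.7% | 66.7% |
| 0.3 | 61.8% | 66.6% |
| 0.5 | 61.2% | 63.6% |
| 0.8 | 50.3% | 51.1% |

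Across these assumptions the share is roughly 50% to 67%. Unscheduled draws would raise the share with any decrease.

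**The case against.** The strongest reply is that the Grade 0 rule speaks of values in a normal range, and a change from baseline has no normal range. Table 9 carries the change as its own row. The rule can therefore be read as reaching only the absolute row and leaving the change row unaddressed. That reading is open, so a reader should not infer that the SAP deliberately overrides Table 9. It does not rescue the plan, though: the SAP then has no graded output for a row that the protocol grades.

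Second, the fall is not hidden. The by-visit summaries give the minimum change, so a drop from 17.0 to 14.5 would show as −2.5 or lower, and every result is listed. This stands, with two limits. A minimum shows the single largest fall in a group, not how many subjects had one. And SAP 7.6 keeps unscheduled results out of summaries, so a fall seen only at an unscheduled visit would appear only in the listings.

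Third, a reader might infer that such subjects drop out of the Grade 3/4 listing. The SAP does not state that listing's grade source, and the Grade 0 wording belongs to the shift-table text, so this is a possibility only.

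Fourth, Table 9 carries the note "Values provided in this table will be included in vaccination pause rules for the trial", from which a reader might infer that pausing decisions were affected. They were not. Protocol 11.1 governs pauses, nothing in the SAP alters it, and the current protocol already describes the single dose as given.

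Fifth, the high Grade 1 share is a property of the adapted scale, under assumed inputs. The SAP adopts nothing that produces it, so it is no charge against the plan as written.

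**Conclusion.** The concern holds as a conflict between a stated SAP rule and a protocol grading row, with no exemption and no declared departure. Its reach is the hemoglobin shift tables and, depending on an unstated choice, the Grade 3/4 listing.

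The size is modest. Under the assumed distributions and lower limits, noise alone would put about 0 to 2 of 250 subjects in the position of an in-range Grade 3 fall. If a vaccine did cause falls of 2.1 to 2.5 g/dL, about 12% to 24% of those affected would be tabulated as Grade 0. The documents give no evidence of such an effect. The arithmetic conflict needs only Table 9 and a normal range that includes the post-dose value; every percentage rests on means, SDs and a lower limit that the documents do not supply.

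The text does not support the stronger claims that graded falls vanish from the report, or that most subjects would be graded 1 under the plan.

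**What to change.** In SAP 10.1.2:
1. State that the Grade 0 rule for in-range values applies only to grades based on the absolute value.
2. Keep the hemoglobin shift table, and say that it uses the absolute-value rows of Table 9.
3. Add an incidence table by vaccine group of each subject's maximum Table 9 change-from-baseline grade. Show all grades, with a note that Grade 1 is expected from noise alone in roughly 50% to 67% of subjects (assumed within-subject SD 0.1 to 0.8 g/dL).
4. Include a subject in the Grade 3/4 listing if either hemoglobin grade reaches 3.

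Giving greater prominence to Grade 2 and above in the new table is a matter of preference, not a requirement.

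The cost is a few lines of SAP text, one small table and a changed listing filter. No new data are needed.

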10.1.3. Vital Signs

Vital sign measurements include heart rate, respiratory rate, systolic blood pressure, diastolic blood pressure, pulse oximetry and temperature, and will be collected at screening, Days 0, 7, 28, 90, 180, and 365. Actual values and changes from baseline will be summarized with descriptive statistics (n, mean, SD, median, minimum, and maximum) by visit. Height, weight, BMI, and Dalhousie Fraility score are only required to be collected at the screening visit and summarized in the demographic and baseline characteristics table.

Vital sign abnormalities are assessed according to the FDA Toxicity Grading Scale (Grade 1, 2, 3, and 4).

Shift tables for each vital sign parameter will summarize the change in the FDA toxicity grades from baseline to the maximum post-baseline (up to end of the main trial) and all visits up to Day 28 by vaccine group, aggregate IVX-A12, and overall. Unscheduled visits will be included. The denominator for percentages is the number of subjects assessed at each parameter and category with a baseline assessment.

All vital sign summaries will be repeated by age subgroup analyses category.

Box plots will be produced for systolic blood pressure and diastolic blood pressure for all ages and timepoints. The y-axis will include the vital sign parameter and unit. The x-axis will include the visit.

All vital sign results will be listed up to end of the main trial, including toxicity grade. A listing including a subset of Grade 3 and Grade 4 results will be provided.

This document is confidential.

10.1.4. Physical Examination

A full physical examination is performed at screening according to the investigator's standard practice. Additional physical examinations may be performed if indicated by review of the subject's medical history. Symptom-directed physical examinations are performed at subsequent visits if deemed necessary, including Days 0, 7, 28, 90, 180 and 365.

Any abnormal findings will be recorded. The clinical significance assessment of each body system ('Normal', 'Abnormal, not clinically significant' and 'Abnormal, clinically significant') will be tabulated.

All physical examination results, up to end of the main trial, will be listed, including details of abnormalities.

10.1.5. ARI Clinical Assessment and Respiratory Diagnostic Testing

ARI Clinical assessment and respiratory diagnostic testing will be listed.

10.2. Observational Extension Trial Safety

The safety analyses will be performed on the EES and will include data during observational extension trial (Visit Day 365 serology date + 1) to end of trial, unless otherwise stated.

10.2.1. Adverse Events

For the observational extension trial, adverse events are collected as SAEs, AESIs, and MAAEs. SAEs, MAAEs and AESIs (including anaphylaxis, thrombocytopenia, and pIMCs, including Guillain Barre's syndrome, as defined in [section 16](#)) from Visit Day 365 of observational extension to end of trial..

AEs resolving during the observational extension trial or start from Visit Day 365 + 1 will be listed.

This document is confidential.

11. Efficacy

11.1. Main Trial Efficacy

The efficacy analyses will be performed on the PPS, unless otherwise stated.

11.1.1. Exploratory Efficacy Analysis

The exploratory endpoint for efficacy is to enumerate the RSV or hMPV cases of mild, moderate, or severe LRTI (CESI) and any severity LRTI by vaccine group from Day 14 (study day 15) post-vaccination up to Day 365 (or end of the Main Trial).

Vaccine efficacy will be calculated as $100 \times (1 - \text{incidence rate ratio})$. The incidence rate for a vaccine group is the number of subjects with a mild, moderate, or severe LRTI due to RSV and/or hMPV divided by cumulative follow-up person time (in years) among all subjects at risk in vaccine group. A subject is considered at risk (and censored) up to the last day of contact while on study or 1st assessment of LRTI (CESI), whichever happens first. The incidence ratio is the ratio between the incidence rates of IVX-A12a to Placebo and IVX-A12d to Placebo. Vaccine efficacy will also be summarized by each severity (mild, moderate, and severe).

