9.1.8 Safety Assessments

Safety assessments: All solicited local (injection site) reactions and systemic ARs are collected for all subjects for 7 consecutive days, starting from the day of the single-dose administration (Day 0) through Day 6 (7 days total); unsolicited AEs through Day 28; and safety blood samples (clinical laboratory evaluation at screening, Day 0/baseline, Day 7, and Day 28).

AEs, SAEs, AESIs ([Section 10.4.4.1](#) and [Appendix D](#)), MAAEs, AEs leading to trial withdrawal, and CESI are captured from the time of randomization to Day 365, approximately 12 months after vaccination. After the Day 365 visit, SAEs, AESIs, and MAAEs will be collected up to the Day 730 visit. Clinic staff (a trained healthcare provider) will contact the subject by phone call or using a digital application (e.g., SMS text) to facilitate the collection of relevant safety information such as concomitant medication use and occurrence of AEs/SAEs. Up to Visit Day 365, all subjects will complete a respiratory symptom surveillance tool approximately twice a week (i.e., approximately twice within 7-day intervals starting on Day 0 post-vaccination) to be monitored for the trial-defined CESI of mild, moderate, or severe LRTI caused by RSV or hMPV, using the established case definition and algorithm for evaluation of ARI and using NP swabs for the detection of RSV, hMPV, and other respiratory viruses. Subjects are instructed to return to the clinic for assessment within 3-7 days of onset of ARI (ideally within 3 days) to maximize detection of virus.

After subjects are unblinded to their trial group assignment at Day 365, consenting IVX-A12a and placebo recipients will be contacted by clinic staff by phone call or with a digital application (e.g., SMS text) to facilitate the collection of MAAEs, AESIs, and SAEs, at Day 545; MAAEs, AESIs and SAEs will also be collected at the clinic visit on Day 730.

Refer to [Section 10.1](#) for safety definitions. Details on collection and reporting of AEs are in [Section 10.5](#).

The solicited ARs included in the safety assessments are listed in [Table 8](#).

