13.1.4 Efficacy Analysis

RSV and/or hMPV cases of mild, moderate, or severe LRTI and any severity LRTI due to RSV and/or hMPV (CESIs), meeting the protocol-specified definitions, will be summarized by vaccine group and placebo group starting on Day 14 through Day 365. Listings will be provided.

Vaccine efficacy will be calculated as $100 \times (1 - \text{incidence rate ratio})$. The incidence rate is the number of subjects meeting the case definition divided by cumulative follow-up person time among all subjects at risk. The incidence rate ratio is the ratio between the incidence rates of vaccine group and placebo group.

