4.1.2. Observational Extension Trial Brief Description

Eligible IVX-A12a and placebo recipients will be invited to enroll into the observational extension portion of the trial, which includes a telephone call at Day 545 (approximately 6 months from Day 365) and a clinic visit at approximately 12 months (Day 730) after the Day 365 visit for a final blood draw. The upper age limit of 85 years was removed.

The observational extension portion of the trial discontinued early, prior to the subjects completing Day 545.

This document is confidential.

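### SAP 11.1.1 gives vaccine-efficacy person-time no Day 14 start and no Day 365 cap; derived literally, it would add unsurveilled time to IVX-A12a and placebo but not to IVX-A12d

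*SAP*

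**What the plan says.** **Cases.** SAP 11.1.1 enumerates CESIs "by vaccine group from Day 14 (study day 15) post-vaccination up to Day 365 (or end of the Main Trial". Protocol 13.1.4 uses the same window: cases are "summarized by vaccine group and placebo group starting on Day 14 through Day 365".

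**Person-time.** In SAP 11.1.1 the rate is the number of subjects with a case "divided by cumulative follow-up person time (in years) among all subjects at risk in vaccine group". The end of risk is set by one sentence: "A subject is considered at risk (and censored) up to the last day of contact while on study or 1st assessment of LRTI" (CESI), whichever comes first. It names no first day of risk and does not mention Day 365. Protocol 13.1.4 also divides by cumulative person-time without giving a start or an end.

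**Contrasts.** "The incidence ratio is the ratio between the incidence rates of IVX-A12a to Placebo and IVX-A12d to Placebo".

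**Surveillance.** Protocol 9.1.8: "Up to Visit Day 365, all subjects will complete a respiratory symptom surveillance tool approximately twice a week". Protocol 10.1.3 ends ARI surveillance at Day 365, and Protocol 10.4.3 ends CESI collection there. The extension schedule in Protocol 2.2 has no symptom tool and no NP swab. SAP 10.2.1 lists only SAEs, AESIs and MAAEs for the extension.

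**Who continues.** SAP 4.1.2: "Eligible IVX-A12a and placebo recipients will be invited to enroll into the observational extension portion of the trial". Protocol 6.3 restricts invitations to subjects in the per-protocol immunogenicity set, and SAP 11.1 runs efficacy on the PPS. SAP 2.2 and 4.1.2 say the extension was discontinued before subjects completed Day 545.

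**The concern.** An incidence rate needs its numerator and denominator to cover the same period. Here the numerator has a stated window and the denominator does not. After Day 365 no CESI can be ascertained, so any later day counted as at risk adds to person-time but can never add a case.

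The mismatch would not fall evenly. IVX-A12d subjects have no on-study contact after the main trial. IVX-A12a and placebo subjects who entered the extension might. Because invitees come from the per-protocol set, the extra time would fall largely inside the set on which efficacy is analysed.

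Placebo is the comparator in both contrasts. If its rate is diluted and the IVX-A12d rate is not, IVX-A12d efficacy is understated for a purely procedural reason. In the IVX-A12a contrast both rates are diluted, and the effect largely cancels when uptake and extra follow-up are alike.

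The missing start day is a smaller gap of the same kind. A subject with a CESI before Day 14 would have risk time that ends before case counting begins, and the SAP does not say how to treat that subject.

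**Working it through.** The documents state no efficacy estimate, case count, attack rate or person-time, so there is no plan figure to reproduce. The check asks how far a literal derivation could move the estimate.

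**Inputs from the documents**
- Case window: Day 14 to Day 365, so B = 365 − 14 = 351 days per subject (SAP 11.1.1).
- VE = 100 × (1 − IRR), each active arm against placebo (SAP 11.1.1).
- No case counted after Day 365; post-Day-365 contact possible only for IVX-A12a and placebo.
- Extension stopped before Day 545. At nominal days, ignoring visit windows, extra time per subject is at most 545 − 365 − 1 = 179 days.

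**Assumptions, because the documents give no figure**
- f, the fraction of an arm with extension contact: 25% to 100%.
- E, extra days to last contact for those subjects: 30 to 179.
- Events rare and dropout negligible.

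**Formulas**
- Person-time inflation in an arm: k = (B + f × E) / B.
- IVX-A12d against placebo: observed IRR = true IRR × k(placebo).
- IVX-A12a against placebo: observed IRR = true IRR × k(placebo) / k(IVX-A12a).

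**IVX-A12d against placebo**

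| E (days) | f | k(placebo) | True VE 50% reads | True VE 0% reads |
|---|---|---|---|---|
| 30 | 0.25 | 358.5/351 = 1.021 | 48.9% | −2.1% |
| 30 | 1.00 | 381/351 = 1.085 | 45.7% | −8.5% |
| 90 | 0.50 | 396/351 = 1.128 | 43.6% | −12.8% |
| 90 | 1.00 | 441/351 = 1.256 | 37.2% | −25.6% |
| 179 | 0.50 | 440.5/351 = 1.255 | 37.3% | −25.5% |
| 179 | 1.00 | 530/351 = 1.510 | 24.5% | −51.0% |

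**IVX-A12a against placebo.** With equal f and E the factors cancel and a true 50% stays 50%. With unequal uptake and E = 179:
- Placebo 0.9, IVX-A12a 0.5: (351 + 161.1)/(351 + 89.5) = 512.1/440.5 = 1.163, so 50% reads 41.9%.
- The reverse: 440.5/512.1 = 0.860, so 50% reads 57.0%.

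**Start day.** With person-time from Day 0, B = 365. In the largest case k is (365 + 179)/365 = 1.490 instead of 1.510, a change of 0.02.

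**After the fix.** With risk time capped at the Day 365 visit, E = 0 and k = 1 in every arm, so true values of 50% and 0% are returned unchanged.

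**The case against.** The strongest reply is that the context already supplies the cap. The rule sits under the main-trial efficacy heading, the preceding paragraph ends the endpoint at Day 365 or the end of the main trial, and SAP 11.2 says the extension has no efficacy endpoints or analyses. The efficacy paragraph of the protocol summary and Protocol 10.1.3 both treat Day 365 as the end of the trial for this endpoint, and SAP 2.2 calls it the final trial visit. A programmer could reasonably stop there. This stands as a plausible reading, but it does not settle the matter. SAP 10.1 and 10.1.1.3 to 10.1.1.5 expressly limit the safety summaries to the end of the main trial, whereas the at-risk sentence refers only to being on study. SAP 8.2 uses study discontinuation for subjects in the extension, and SAP 10.2 lets the end of the trial include it. Ruling out an extension efficacy analysis does not say how the main-trial one is censored.

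Second, the extra time is not shown to exist. The only scheduled extension contacts after Day 365 were Days 545 and 730, and the extension ended before the first was completed. Later contacts could come only from discontinuation or unscheduled contact, whose dates are not given. This stands: the size is a range under assumptions, not an estimate.

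Third, little rests on the result. Efficacy is exploratory and SAP 7.1 tests no hypotheses. With assumed counts of 2 cases in 50 placebo and 2 in 100 IVX-A12d subjects, VE is 50% with an exact 95% interval of roughly −590% to 96%, far wider than any shift in the table. This also stands; it limits the importance of the point but does not justify an open censoring rule.

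A reader might go further and infer that the choice between formulations is distorted. The documents do not support that. Protocol 4.4 records that IVX-A12a was selected from the Day 28 interim and Phase 1 data, and SAP 11.1.1 plans no efficacy contrast between the two active arms.

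**Conclusion.** The point holds as a gap in specification. The case window and the at-risk rule in SAP 11.1.1 do not match, and a literal derivation would add unsurveilled person-time to IVX-A12a and placebo only. IVX-A12d efficacy against placebo would then be understated; IVX-A12a against placebo would change little if uptake and extra follow-up are similar.

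The size cannot be determined from the documents. Across the assumed ranges of uptake and extra days, the inflation of about 1.02 to 1.51 would turn a true 50% into about 49% to 25%, and a true 0% into about −2% to −51%.

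It would be tempting to say that the bias is present. The documents do not show this: they do not reveal which censoring date was programmed, and the context may imply a cap. The missing start day is also of little practical weight, since Protocol 4.4 reports no CESI through Day 28. The point is worth correcting because the written rule can produce a wrong rate and the correction is cheap.

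**What to change.** In SAP 11.1.1, replace the at-risk sentence with wording to this effect:

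> Person-time runs from Day 14 (study day 15), matching the case window, to the earliest of the first assessment of CESI, the last main-trial contact, and the Day 365 visit or end of the Main Trial. Extension contacts do not contribute.

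This keeps the SAP's first-assessment date as the event date; nothing here calls for moving it to symptom onset.

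The cost is one sentence and a check of the censoring-date derivation, with no new data. SAP section 12 shows that outputs had already been completed when a late table and listing were added, so if the derivation used extension contacts or a different start day, the efficacy outputs would need to be re-run. If it already ran from Day 14 and stopped at Day 365, no result changes.
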